8.8 Pregnancy Reporting

All positive urine pregnancy tests will be recorded during screening and at the end of the study or early termination in the study. Women who screen positive for pregnancy will be encouraged, if not already scheduled or completed, to see their primary health care provider or obstetrician for a serological confirmatory test and to be followed thereafter by their obstetrician per best practice guidelines.

Pregnant women and women who may become pregnant during the study will be permitted to participate in the study since RD-X19 presents no possible exposure or hazard to germline cells or developing embryo or fetus.

9.0 STATISTICAL CONSIDERATIONS

9.1 Primary Endpoint and Key Secondary Endpoint

Primary Endpoint

The primary endpoint will be time to sustained resolution of COVID-19 signs and symptoms without subsequent symptom recurrence or disease progression until the end of the study.

Resolution of COVID-19 signs and symptoms is defined as cough, sore throat, nasal congestion, headache, chills and/or sweats, myalgia, fatigue, and nausea (with or without vomiting) having been assessed by the subject as absent (0) or mild (1) and temperature is less than 100.5 °F.

Sustained resolution of COVID-19 signs and symptoms is achieved when all signs and symptoms are resolved for five consecutive assessments (corresponding to an approximately 48-hour period).

	Page 52 of 70
EmitBio Inc.	Version: 3.1
EB-P30-01	7 February 2024

After sustained resolution is achieved, symptom recurrence is defined as having three or more consecutive assessments (corresponding to an approximately 24-hour period) where two or more of the nine signs and symptoms do not meet the resolution condition.

"Disease progression" is defined as having evidence of involvement of the lower respiratory tract: shortness of breath (defined as respiratory rate of 20 or more breaths per minute) and SpO2 < 96% (both ascertained from the average of three replicate assessments) and/or pulmonary imaging demonstrating COVID-19 pneumonia.

Key Secondary Endpoint:

The key secondary endpoint will be time to the first of two consecutive negative SARS-CoV-2 antigen tests (with a minimum time between tests of 6 hours) without subsequent virological rebound during the subject's remaining time on study. Virological rebound (after having achieved two such consecutive negative tests) is defined as having two or more positive tests out of three consecutive assessments.

9.2 Power and Sample Size:

For Mild subjects (including the additional requirement that baseline heart rate < 90, as in the FDA definition of mild COVID-19 [18]) age 40 or older in the EB-P20-01 trial, the hazard ratio in the full analysis set (FAS) was 0.62. Assuming an overall type 1 error of 0.025 one-sided a total of 228 events for the primary endpoint gives 95% power for this hazard ratio of 0.62 and also gives 90% power for a hazard ratio of 0.65, as well as 80% power for a hazard ratio of 0.69.

A total of 326 subjects will be initially randomized 1:1 (to RD-X19 and Sham) and this will give approximately 228 events assuming that 90% of RD-X19 subjects and 50% of Sham subjects will have the event. Section 9.4.3, Interim Analysis, describes a blinded sample size review that will be carried out based on the pooled event rate, after which the number of randomized subjects could potentially be increased.

9.3 Analysis Populations:

Three analysis populations are defined as follows:

- Full Analysis Set (FAS) which will consist of all randomized subjects. This population will be the primary analysis population for all efficacy endpoints. Subjects will be analyzed on the basis of the treatment to which they were randomized.
- Safety Population which will consist of all randomized subjects who received any study treatment. This population will be the primary analysis population for all safety analyses. Subjects will be analyzed on the basis of the treatment that they received.
- Per Protocol (PP) Population will exclude from the FAS: (i) study subjects who experienced one or more of a pre-specified subset of major protocol deviations/protocol violations while on study, and (ii) subjects who did not meet certain pre-specified criteria concerning number of treatments received. The full list of reasons for exclusion from the FAS population will

EB-P30-01	7 February 2024
EmitBio Inc.	Version: 3.1
	Page 53 of 70

be defined in the Statistical Analysis Plan prior to unblinding. Protocol deviations are not exclusionary for the PP population. Major deviations/violations will be defined within the Statistical Analysis Plan prior to unblinding.

• Protocol deviations/violations are defined in the Definitions Section.

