9.4.3 Interim Analysis

A blinded sample size review will be carried out by an independent statistician based on the first 164 randomized subjects after the last of these subjects has reached the Day 14/ET visit. The pooled proportion (p_{OBS}) of subjects with an event will be determined and if this is less than 0.70 then in order to obtain approximately 228 events at the end of the study the total number of randomized subjects will be increased to 326 * 0.70/poBs (rounded up to the nearest multiple of 2, due to the 1:1 active:sham randomization) subject to a cap of 380. The number of randomized subjects will not be decreased, and no unblinded assessment of efficacy will be carried out at this time.

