#### **3.3.** DETERMINATION OF SAMPLE SIZE

The sample size was based on the primary end point of time to sustained symptom resolution. In the EB-P20-01 trial, for subjects aged 40-years-old or over with mild disease (based on the NIH and FDA definition of mild COVID-19), the hazard ratio for this endpoint in

<sup>1 The COVID-19 Composite Severity Score at baseline is defined as the sum of the eight individual COVID-19 symptom severity scores divided by eight.

the full analysis set (FAS) was 0.62. Assuming an overall (one-sided) type 1 error of 0.025, a total of 228 events for the primary endpoint gives 95% power for a hazard ratio of 0.62 and also gives 90% power for a hazard ratio of 0.65, as well as 80% power for a hazard ratio of 0.69.

A total of 326 subjects will be initially randomized 1:1 (to RD-X19 and Sham) which will result in approximately 228 events assuming that 90% of RD-X19 subjects and 50% of Sham subjects will have the event.

A blinded sample size review will be carried out by an independent statistician based on the first 164 randomized subjects, with the objective of seeing whether the sample size needs to be increased. See Section 8.1 for details.

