#### 8.2.1. NPANCOVA ANALYSIS

Ties will be handled using Efron's method [9].

The primary endpoint is time-to-event in nature and will be analysed using the nonparametric randomization-based covariate adjustment method of Saville and Koch (2013) [10] which is expanded to handle stratified randomisation by Hussey et al (2016) [11]. They refer to this method as NPANCOVA, and this naming will be preserved here.

NPANCOVA avoids the assumption of proportional hazards for each of the covariates. It does rely on the assumption of proportional hazards for the treatment effect as obtained from an unadjusted Cox proportional hazards model (with a single term for treatment and no covariates), but as is well known the p-value associated with this unadjusted estimate is comparable to the p-value obtained from the nonparametric log-rank test.

The method also does not make any assumptions about the relationship between the covariates and the outcome. The log hazard ratio can be viewed as a stratified population-averaged estimate.

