#### Step One

The NPANCOVA method begins by fitting a stratified treatment-only Cox proportional hazards model. The model formula is:

$$\lambda(t; z_{hij}) = \lambda_{0h}(t) \times \exp(\beta z_{hij})$$
(1)

Where  $\lambda(t; z_{hij})$  is the hazard at time t for subject j in stratum h in treatment group i, where in this case  $h \in \{1,2,3,4\}, i \in \{1,2\}$ , and  $j \in \{1,2, ..., n_{hi}\}$ , where  $n_{hi}$  is the number of randomized subjects in treatment group i in that stratum.  $\lambda_{0h}(t)$  is the baseline hazard function for stratum h, and  $z_{hij}$  is the treatment group indicator for subject j in stratum h in treatment group i, which takes on a value 1 for the RD-X19 treatment group and 2 for the sham treatment group. In the next step, the Cox model from which DFBETA is obtained will have RD-X19 as the reference.

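### The planned event rates of 90% (RD-X19) and 50% (sham) imply a hazard ratio of about 0.30 under proportional hazards, not the 0.62 to 0.69 used for power

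*Protocol*

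**What the plan says.** Protocol 9.2 sets a one-sided type 1 error of 0.025 and states that "a total of 228 events for the primary endpoint gives 95% power for this hazard ratio of 0.62". It adds 90% power at 0.65 and 80% power at 0.69. The value 0.62 is the full analysis set estimate from the EB-P20-01 trial in mild subjects aged 40 or older.

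The next step sets the number of subjects. With 326 randomized 1:1, "this will give approximately 228 events assuming that 90% of RD-X19 subjects and 50% of Sham subjects will have the event". SAP 3.3 repeats this: "which will result in approximately 228 events assuming that 90% of RD-X19 subjects and 50% of Sham subjects will have the event".

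The average of the two rates, 0.70, is the trigger for the blinded sample size review (Protocol 9.4.3, SAP 8.1). If the pooled rate in the first 164 subjects is below 0.70, the sample size rises to 326 × 0.70 divided by the observed rate, "subject to a cap of 380".

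On the analysis, SAP 8.2.1 Step One says "The NPANCOVA method begins by fitting a stratified treatment-only Cox proportional hazards model" and that "the Cox model from which DFBETA is obtained will have RD-X19 as the reference". The hazard ratio is therefore sham over RD-X19, and a value below 1 favours RD-X19. On proportional hazards, SAP 8.2.1 says: "It does rely on the assumption of proportional hazards for the treatment effect".

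**The concern.** The power statement and the event-to-subject conversion stand next to each other and describe different treatment effects. A hazard ratio near 0.65 is a moderate effect. Event rates of 90% and 50% over the same 14 days are a much larger one.

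The 90%/50% pair is the only stated basis for the pooled 0.70, and so for both the 326 subjects and the review trigger. No source is given for either rate. If one of them is wrong, the expected number of events from 326 subjects moves, and the direction depends on which one. At stake is whether 326, with a ceiling of 380, can be expected to deliver the 228 events on which the stated power rests.

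**Working it through.** **Inputs.** From Protocol 9.2 and SAP 3.3: one-sided 0.025, 228 events, hazard ratios 0.62/0.65/0.69, 326 subjects (163 per arm), event rates 90% and 50%. From Protocol 9.4.3 and SAP 8.1: trigger 0.70, rounding up to an even number, cap 380. Both arms follow the same 14-day schedule.

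**1. The plan's own figures reproduce.**

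- Events: 163 × 0.90 + 163 × 0.50 = 146.7 + 81.5 = 228.2, the same as 326 × 0.70.
- Events needed by the Schoenfeld formula, 4(z_α + z_β)²/(ln HR)²: 227.5, 226.5 and 228.0 for the three hazard ratio and power pairs.
- Power at 228 events, Φ(|ln HR|·√d/2 − 1.96): 95.0%, 90.2% and 80.0%.

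**2. The hazard ratio implied by 90% and 50%.** Under proportional hazards with common follow-up, the hazard ratio is the ratio of cumulative hazards:

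HR = ln(1 − 0.50)/ln(1 − 0.90) = 0.693/2.303 = 0.301.

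This is less than half of any planning value.

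**3. Keep sham at 50%.** The matching RD-X19 rate is 1 − 0.50^(1/HR).

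| | HR 0.62 | HR 0.65 | HR 0.69 |
|---|---|---|---|
| RD-X19 rate | 67.3% | 65.6% | 63.4% |
| Pooled rate | 58.7% | 57.8% | 56.7% |
| Events from 326 | 191 | 188 | 185 |
| Power at 326, no review | 91.1% | 84.0% | 71.3% |
| Size the review asks for | 390 | 396 | 404 |
| Events at the cap of 380 | 223 | 220 | 215 |
| Power at the cap | 94.6% | 89.1% | 77.7% |
| Loss against stated power (points) | 0.4 | 0.9 | 2.3 |

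The cap can still deliver 228 events only while the pooled rate is at least 228/380 = 0.60. All three pooled rates fall below that.

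**4. Keep RD-X19 at 90%.** The matching sham rate is 1 − 0.10^HR.

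| | HR 0.62 | HR 0.65 | HR 0.69 |
|---|---|---|---|
| Sham rate | 76.0% | 77.6% | 79.6% |
| Pooled rate | 83.0% | 83.8% | 84.8% |
| Events from 326 | 271 | 273 | 276 |
| Power | 97.6% | 94.5% | 87.0% |

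**5. Keep the pooled rate at 0.70.** The RD-X19/sham pairs that average 0.70 are 78.5%/61.5% at 0.62, 77.7%/62.3% at 0.65 and 76.7%/63.3% at 0.69.

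**6. Could censoring explain the gap?** Assume exponential event and censoring times, RD-X19 at 90%, and censoring in the sham arm only. Then about 43%, 44% or 45% of sham subjects would have to be censored before the end of follow-up to bring the crude sham rate down to 50% at the three hazard ratios. Neither document plans for this.

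**The case against.** The strongest reply has four parts.

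- **The rates are crude proportions.** The plan uses 90% and 50% only to convert events to subjects and never derives a hazard ratio from them. Crude rates also absorb withdrawal, recurrence, antiviral use and hospitalization. This is a fair reason to state the conflict conditionally. It does not close the gap, because step 6 shows how much sham-only censoring would be required. Nor does the test itself need proportional hazards, since the SAP notes that "the p-value associated with this unadjusted estimate is comparable to the p-value obtained from the nonparametric log-rank test". The event-based power figures and the reported hazard ratio do rest on it.
- **Only the pooled rate matters, and it is monitored.** Power depends on total events, and the blinded review measures the pooled rate and raises the sample size. This stands. It is why the 71% to 91% power figures at 326 should not be read as the expected result: they apply only if the review is ignored.
- **Table 1 of the protocol makes the shortfall less likely.** Sham median times to sustained resolution were 170.3 h (age 40-49) and 241.2 h (age 50-65), well inside the 14 days. With exponential times (an assumption), sham rates would be 56% to 69% at 288 h and 62% to 75% at 336 h. At HR 0.62 the pooled rate is then 0.65 to 0.77 at 288 h and 0.70 to 0.82 at 336 h, above the 0.60 that the cap can absorb. This also stands, with the caveats that the table does not confirm an identical endpoint definition and that crude rates run below Kaplan-Meier rates. It supports 0.70 as a pooled figure, but it undercuts the stated 50% and does not rescue the 90%/50% pair.
- **Covariate adjustment could recover the loss.** A variance reduction of about 2.2%, 3.7% or 5.5% would offset the loss at the cap. The plan states no expected gain, so it cannot be counted on, but the losses in step 3 are unadjusted figures.

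**Conclusion.** The concern holds, as a minor point. Under proportional hazards with equal follow-up and no differential censoring, the two arm rates imply a hazard ratio of 0.30, against planning values of 0.62 to 0.69. The documents state nothing that would reconcile the two.

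The consequence is limited. The 228-event target and its power are correct. The direction of the error is not fixed: expected events from 326 range from 185 to 276, depending on which rate is kept. In the unfavourable case the loss after the review is 0.4 to 2.3 percentage points of power, and Table 1 suggests that this case is the less likely one. The finding does not show that 326 is too small. It shows that the stated reason for 326 and for the 0.70 trigger does not agree with the effect size used for power.

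**What to change.** In Protocol 9.2 and SAP 3.3, do one of two things:

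- replace 90%/50% with arm rates that match the planning hazard ratio, and give their source; or
- state the non-proportional pattern that makes 90%/50% compatible with the planning hazard ratios.

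Then restate expected events and power from the chosen rates. The pairs in step 5 illustrate rates that keep the pooled 0.70; they are not recommended values. If the 50% sham rate is kept, report expected events and power at the 380 cap as well (223/220/215 events; 94.6%/89.1%/77.7%).

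The cost is wording in two sections. No subjects are added, and 326, the 0.70 trigger, the cap, the blinded review and the analysis are unchanged.

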9.4 Statistical Analyses

9.4.1 Efficacy Analyses

Details on Derivation of the Primary Endpoint

The primary endpoint is defined in Section 9.1, Primary Endpoint, and this current section provides further details on the exact derivation of this endpoint.

The eight symptoms included in the definition of the primary endpoint are cough, sore throat, nasal congestion, headache, chills and/or sweats, myalgia, fatigue, and nausea (with or without vomiting). The single sign included in the definition of the primary endpoint is temperature. Together these nine signs and symptoms are used to define resolution.

The first step in derivation of the primary endpoint is at each of the twice-daily assessments at which the subject records signs and symptoms in the e-diary to classify subjects on the basis of which of the following applies:

- (i) Success (S), which corresponds to resolution, if all of the above eight symptoms are graded with a severity score of 0 (absent) or 1 (mild), and temperature $< 100.5^{\circ}$ F;
- (ii) Failure (F_n) if n (≥1) of the nine signs and symptoms do not meet the condition described in
 (i) above;
- (iii) Disease progression (D) if the subject has $RR \ge 20/min$ and SpO2 < 96% (both based on the average of three replicate assessments over 10 minutes) and
- (iv) Missing (M) if the subject did not record all signs and symptoms entries in their e-diary at this timepoint.
- Note: For subjects that at a particular timepoint are missing data for a subset of their nine signs and symptoms the data handling rules will be described in the SAP.

To achieve "sustained resolution" a subject must first record five consecutive timepoints (corresponding to an approximately 48-hour period) at which the signs and symptoms have resolved (i.e., assessment results SSSSS).

Time to sustained resolution of COVID-19 signs and symptoms is the time (in hours) of the first "S" in a sequence "SSSSS" for which there is no subsequent symptom recurrence and no subsequent disease progression during the subjects' remaining time on study.

After recording "SSSSS" a subject is defined to have had symptom recurrence if there are three (corresponding to an approximately 24-hour period) or more consecutive values of F_n with $n \ge 2$ in

	Page 54 of 70
EmitBio Inc.	Version: 3.1
EB-P30-01	7 February 2024

each case, i.e., three or more consecutive assessments where two or more of the nine signs and symptoms do not meet the condition described in (i) above.

A subject is defined to have had subsequent disease progression if, after recording "SSSSS", they have "D" (disease progression) at even a single timepoint, or if pulmonary imaging demonstrates COVID-19 pneumonia

Note: A subject that has symptom recurrence and/or disease progression is still eligible to later have the event for the primary endpoint, if they subsequently have five consecutive assessments at which the signs and symptoms have resolved ("SSSSS"), but with no further subsequent rebound or subsequent disease progression during the subjects' remaining time on study.

Analyses of the Primary Endpoint

The method of primary analysis for the primary endpoint is nonparametric randomization-based covariate adjustment for time-to-event outcomes using Efron's method for handling ties, with stratification by the design's stratifications factors (age category [40-49, \geq 50] and baseline disease severity score [<1.25, \geq 1.25]), and with between one to four pre-specified (in the SAP) prognostic baseline covariates to improve precision of the estimate of the hazard ratio. This analysis will be based on the methods of Saville and Koch [20] as extended to stratified analyses by Hussey et al [21]. Testing for treatment will be carried out at the 5% two-sided significance level, and 95% two-sided confidence interval (CI) for the hazard ratio will also be derived. This primary analysis will be based on the FAS.

The non-parametric Kaplan-Meier method will also be used for the FAS to estimate the survival curves, within the plot of which the number of subjects at risk will also be displayed. The median survival time will be estimated for each treatment group, together with its 95% CI using the Brookmeyer & Crowley method [19]. Estimates of the 25th and 75th percentiles will also be derived together with their corresponding 95% CIs.

A secondary analysis will be carried out on the FAS for the primary endpoint based on a Cox Proportional Hazards model, using Efron's method for handling ties, including the same stratification factors and covariates as included in the primary analysis. In the analyses described above the following rules for event times and censoring will be implemented:

- (i) Subjects that are hospitalized will be censored at 360 hours (which corresponds to the end of the time window for the Day 14 visit) and this rule takes precedence over all other rules;
- (ii) A subject that records "SSSSS" i.e., five consecutive timepoints (corresponding to an approximately 48-hour period) at which the signs and symptoms have resolved who does not have any subsequent symptom recurrence or subsequent disease progression during the subject's remaining time on study, will have the event at the time of the first "S" in this sequence;

	Page 55 of 70
EmitBio Inc.	Version: 3.1
EB-P30-01	7 February 2024

- (iii) A subject not satisfying case (i) or (ii), who takes nirmatrelvir/ritonavir or molnupiravir after initiating study treatment will be censored at the time that they first took this antiviral medication; and
- (iv) Subjects not satisfying case (i), (ii), or (iii) will be censored at the last time that they have e-diary data recorded.
- Note: Subjects taking nirmatrelvir/ritonavir or molnupiravir after initiating study treatment must have recorded "SSSSS" (or equivalent) prior to starting this antiviral medication to be counted under case (ii), and if not then they will be counted under case (iii).

Further details on data handling rules will be provided in the SAP.

Supportive analyses for each of the methods described in this section will also be carried out for the PP population. Further sensitivity analyses for the primary endpoint will be described in the SAP.

Analyses of the Key Secondary Endpoint

At each of the twice-daily assessment times at which the subject is scheduled to take the SARS-CoV-2 antigen test the results will be either Negative (N), Positive (P), Inconclusive (I) or Missing (M).

The first step in defining the key secondary endpoint is to identify cases that will be counted as having "two consecutive negative SARS-CoV-2 antigen tests". The following sequences will be counted as satisfying this condition: (a) "NN" and the two tests are at least six hours apart; (b) multiple consecutive "N" values where the first and last must be at least six hours apart; or (c) "N" followed by up to three "M" or "I" values followed by "N" where the two "N" values must be at least six hours apart. In the remainder of Section 9.4.1.3 the use of "NN" will be refer to any of cases (a)-(c).

The second step is to identify cases that are counted as subsequent virological rebound which is defined as "having two or more positive tests out of three consecutive assessments". This would include "PPP", "PPN", "PNP", "NPP", or "PP". In addition, if a "P" is followed by an "M" or "I" then the "P" will be carried forward so that this will also be counted as a rebound.

The key secondary endpoint is then calculated as time to first of two consecutive negative SARS-CoV-2 antigen tests (with a minimum time between tests of 6 hours) without subsequent virological rebound, during the subjects' remaining time on study. Subsequent virological rebound is defined as having two or more positive tests out of three consecutive assessments.

The following rules for event times and censoring of the key secondary endpoint will be implemented:

(i) Subjects that are hospitalized, who progress to more severe forms of COVID-19, or who require therapy with an FDA-authorized COVID-19 treatment will be censored at 360 hours (which corresponds to the end of the time window for the Day 14 visit) and this rule takes precedence over all other rules;

(ii) A subject that records "NN" based on two tests at least six hours apart without subsequent rebound during the subject's remaining time on study will have the event at the time of the first "N" in

Confidential Information; this Protocol is Confidential and Proprietary to EmitBio Inc.

this sequence, and

(iii) Subjects not satisfying case (i) or (ii) will be censored at the time of their last self-assessment /diagnostic test.

The primary analysis of this key secondary endpoint will be nonparametric randomization-based covariate adjustment for time-to-event outcomes using Efron's method for handling ties, with stratification by the design's stratifications factors, and with the same 1-4 pre-specified prognostic baseline covariates as included in the primary analysis of the primary endpoint. The 95 % two-sided CI for the hazard ratio will also be derived. The primary analysis will be based on the FAS. In addition, the same Kaplan-Meier-based analyses as described for the primary endpoint will also be provided for this key secondary endpoint.

A secondary analysis of this key secondary endpoint will be carried out on the FAS based on a Cox Proportional Hazards model, using Efron's method for handling ties, including the same stratification factors and covariates as included in the primary analysis of this endpoint.

Multiplicity Adjustment

The key secondary endpoint will only be formally tested if statistical significance has been obtained for the primary endpoint. This step-down procedure ensures that there will be strong control of the experiment-wise type 1 error across the primary endpoint and the key secondary endpoint.

